COMIRB Protocol

COLORADO MULTIPLE INSTITUTIONAL REVIEW BOARD
[name] [contact] [contact]

Protocol #: 16-1965

Project Title: Management of diabetic ketoacidosis in children: does early glargine prevent rebound hyperglycemia?

Short Title: "Early glargine in DKA"

Principal Investigator: [name]

Co-investigators: [name] [name]; [name], PhD

Version Date: 11/6/2017

I. Hypotheses and Specific Aims:

Hypothesis 1 (Primary outcome): Early administration of glargine in the treatment of DKA in children will result in reduced rebound hyperglycemia compared to those given standard-of-care management.

Specific Aim 1 (Primary outcome): To evaluate the rate of rebound hyperglycemia (serum glucose level of greater than 180 mg/dL (>10 mmol/L) within 12 hours after discontinuation of IV insulin) in children treated for diabetic ketoacidosis (DKA) with early glargine versus standard-of-care management.

Hypothesis 2: Early administration of glargine in the treatment of DKA in children will result in a reduced rate of recurrent ketogenesis compared to those given standard-of-care management.

Specific Aim 2: To evaluate the rate of recurrent ketogenesis (beta-hydroxybutyrate ≥ 1.5 mmol/L within 12 hours after discontinuation of IV insulin) in children treated for diabetic ketoacidosis (DKA) with early glargine versus standard-of-care management.

Hypothesis 3: The risk of hypoglycemia will not differ between those given early administration of glargine versus those given standard-of-care management:

- a. Early administration of glargine in the treatment of DKA in children will not increase hypoglycemic events compared to those given standard-of-care management.
- b. Rate of blood glucose decrease while on IV insulin in children with DKA will not be different between those given early administration of glargine versus those given standard-of-care management.
- c. Participants who received early glargine will not need more frequent reductions in the IV insulin rate than those given standard-of-care management.

Specific Aim 3: To determine the risk of hypoglycemia between those given early administration of glargine versus those given standard-of-care management.

- a. Assess the frequency of hypoglycemic events during treatment of DKA, and within 12 hours after discontinuation of IV insulin, in children given early glargine versus standard-of-care management.

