 - Percent of patients with blood glucose > 180 mg/dL.
 - Median blood glucose.
 - Percent of time with blood glucose > 180 mg/dL.
2. Rate of recurrent ketogenesis (serum beta-hydroxybutyrate \geq 1.5 mmol/L) within 12 hours (or until time to hospital discharge if less than 12 hours) after discontinuation of IV insulin.
 - Rate of late-recurrent ketogenesis (serum beta-hydroxybutyrate \geq 1.5 mmol/L) 12-18 hours after discontinuation of IV insulin for participants who remain hospitalized for over 24 hours.
3. Frequency of hypoglycemic events while on IV insulin (and within 12 hours after discontinuation of IV insulin) on glucometer or CGM.
 - Glucometer: percent of patients with blood glucose < 70 mg/dL (+/- 2 hours of an "index" hypoglycemic event).
 - CGM: % of time with blood glucose < 70 mg/dL.
4. Rate of blood glucose decrease while on IV insulin on glucometer and CGM within the following time points: 0-2 hours, 2-4 hours, 4-6 hours, >6 hours.
5. Number of participants who needed a decrease in their IV insulin rate (secondary to hypoglycemia).
6. Feasibility of using CGM as a tool for glucose monitoring in DKA.
 - Percent of CGM failures during treatment of DKA.
 - Correlation of CGM to POC glucose monitoring during DKA.

B. Description of Population to be Enrolled:

Eligible patients will be enrolled from Children's Hospital Colorado Emergency Department; a large tertiary care ED and level I trauma center in Aurora, Colorado. These will be patients with either a known diagnosis of T1D presenting in DKA or a new diagnosis of T1D presenting in DKA (see inclusion criteria). Patients will be enrolled either by the PI or a member of the study team (who will be available between the hours of 8:00 am and midnight). Depending on study team member availability, and due to the variability of time of presentation to the ED, patients who present outside of these hours may not be able to be enrolled into the study.

In this study we aim to approach 100 participants, both males and females aged 6-17.99 years, who present in DKA. Assuming 80% of participants approached will be eligible to participate and 60% of eligible subjects will consent to participate, this provides at least 48 subjects, which is needed for 80% power to detect an absolute difference of 40% difference in the rate of rebound hyperglycemia.

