- Lab collection: serum glucose, serum bicarbonate, serum sodium, serum chloride, serum potassium, serum blood urea nitrogen, serum creatinine, and serum beta-hydroxybutyrate will be obtained using standard venipuncture methods per hospital policy by trained staff. These measurements will be determined using standard methods in the Children's Hospital Colorado core laboratory. Blood glucose and beta-hydroxybutyrate will also be obtained using a point-of-care meter per hospital policy or at the Barbara Davis Center.

DKA protocol: Aside from the timing of glargine administration, all other treatment of DKA will be per the standard hospital DKA protocol (clinical care guidelines) at Children's Hospital Colorado. Available at: <https://ccguidelinesportal.childrenscolorado.org/guidelines/>

Glargine administration: This is a long-acting insulin analog which could theoretically increase the risk of hypoglycemia during its duration-of-action (20-24 hours). However, this is standard therapy for type 1 diabetes management with a long history of safe use. As such, study participants will receive glargine regardless of which study group they are randomized to; the only difference being the timing of glargine administration. Further, one of our secondary outcomes is to determine the risk of hypoglycemia between those given glargine early in DKA management versus those given glargine at time of DKA resolution.

CGM data collection: Wearing a CGM will be optional for study participants and included in the protocol as funding allows. The CGM sensor will be placed by trained study personnel to reduce risk of injury and/or sensor malfunction and to improve compliance. The CGM data will be downloaded after 1 week using standard industry software by trained staff or study personnel and the information stored in a locked study office.

Plan to minimize risk:

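### Aim 3a is about the frequency of hypoglycemic events, but the glucometer measure counts patients with a low, its +/- 2 h clause is undefined, and no measure counts all lows in all participants

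*Combined protocol and SAP*

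**What the plan says.** All references are to the combined protocol and SAP.

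- **Section I, Hypothesis 3a:** "Early administration of glargine in the treatment of DKA in children will not increase hypoglycemic events compared to those given standard-of-care management".
- **Section I, Specific Aim 3a:** "Assess the frequency of hypoglycemic events during treatment of DKA, and within 12 hours after discontinuation of IV insulin".
- **Section IV.A, secondary outcome 3, heading:** "Frequency of hypoglycemic events while on IV insulin (and within 12 hours after discontinuation of IV insulin) on glucometer or CGM".
- **Section IV.A, secondary outcome 3, first measure:** "Glucometer: percent of patients with blood glucose < 70 mg/dL (+/- 2 hours of an" index hypoglycemic event). The clause is not defined here and does not appear again.
- **Section IV.A, secondary outcome 3, second measure:** "CGM: % of time with blood glucose < 70 mg/dL".
- **Section IV.D:** "Wearing a CGM will be optional for study participants and included in the protocol as funding allows".
- **Section V:** the halting criteria compare numbers of severe hypoglycemic events between arms and give no figure. Severe means a value below 70 mg/dL that leads to a seizure, glucagon or an IV dextrose bolus.
- **Section VII:** a chi-squared test is named for rebound hyperglycemia, and CGM summaries, including time below 60 and 70 mg/dL, are compared between groups. No test and no event count are named for glucometer hypoglycemia.

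**The concern.** The hypothesis, the aim and the outcome heading speak of events or their frequency. The one hypoglycemia measure available for every participant is a yes/no per child, which cannot register recurrence.

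This matters because the hypothesis is one of no increase. Section IV.D accepts that glargine could in theory raise the risk of hypoglycemia over its 20-24 hours of action, and under Section IV.C.2.1 the early arm can receive it while IV insulin is running. Repeated lows in the same children are a plausible form of harm. If the excess took that form, the glucometer measure would lean toward the reassuring answer.

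The +/- 2 h clause adds a second difficulty. Because its meaning is not given, two analysts could handle the same readings differently.

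**Working it through.** **1. Units, side by side.**

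| Place | Unit |
|---|---|
| Hypothesis 3a | events |
| Aim 3a | frequency of events |
| Outcome 3, heading | frequency of events |
| Outcome 3, glucometer | patients (yes/no) |
| Outcome 3, CGM | percent of time, sensor wearers only |
| Outcome 5 | participants needing an insulin-rate decrease |
| Halting rule | number of severe events only |

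No row counts all lows in all participants.

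**2. What the +/- 2 h clause could do.** If it groups readings around an index low into one episode, a child with lows at hours 1, 2 and 8 has two episodes, but is still one affected patient. The clause then has no effect on an any-low percentage. If it requires another low within 2 h of the index low, a child with a single low no longer counts, and the percentage changes. The text does not say which is meant.

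**3. The plan's own figure.** Table 1 in Section VII gives a total of 48 for 30% v 70% rebound hyperglycemia (two-sided 0.05, 80% power):

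n per arm = [1.96 × √(2 × 0.5 × 0.5) + 0.842 × √(0.3 × 0.7 + 0.7 × 0.3)]² / 0.4² = 23.3, rounded up to 24, so 48 in total.

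This reproduces, but it concerns the primary outcome. The documents give no rate, repeat count or margin for hypoglycemia, so everything below rests on assumed inputs.

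**4. Single illustration (assumed).** 24 per arm, 6 affected in each, 1 episode per affected child in control and 2.5 in the early arm.

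- Percent of patients: 6/24 = 25% v 6/24 = 25%, Fisher p = 1.0.
- Episodes: 6 × 1 = 6 v 6 × 2.5 = 15, ratio 15/6 = 2.5.

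**5. Range (assumed).** Let a share p of 10-40% have any low in both arms, with 1 episode per affected control child and k = 2 or 3 per affected early-arm child. The difference in percent of patients is 0 points throughout. Episodes per 100 children are 100p in control and 100pk in the early arm: 10-40 v 20-80 at k = 2, and 10-40 v 30-120 at k = 3.

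**6. Chance of a significant result at 24 per arm.** Simulation with 4,000 runs per setting, p = 20-40% in both arms, and episodes per affected child equal to 1 + Poisson:

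| Measure | ratio 2 | ratio 3 |
|---|---|---|
| Percent of patients (chi-squared) | 5-6% | about 5% |
| Episode rate (robust log rate ratio) | 17-39% | 38-75% |

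The first row is simply the false-positive level. With no true difference, the episode-rate test rejected in 1-4% of runs, so its figures are not inflated by excess false positives.

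**7. Precision of the 6 v 15 example.** Split the 15 episodes as 2, 2, 2, 3, 3, 3. Means per child are 6/24 = 0.25 and 15/24 = 0.625; sample variances are 0.196 and 1.288.

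SE(log ratio) = √[0.196/(24 × 0.25²) + 1.288/(24 × 0.625²)] = √(0.130 + 0.137) = 0.52.

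95% CI = exp(ln 2.5 ± 1.96 × 0.52), about 0.9 to 7. The permutation p for this split is 0.19. An unclustered binomial split of 15 out of 21 gives p = 0.078. More uneven splits give wider intervals.

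**The case against.** **Percent of patients is a legitimate measure.** The parent Hypothesis 3 and Aim 3 speak of the risk of hypoglycemia, and the share of children affected is a standard summary of risk. The primary outcome likewise expresses a rate as a percent of patients. This stands. A reader might infer that the glucometer measure does not test the hypothesis at all; the documents do not support that. It tests the risk form and leaves the event-frequency form open.

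**Other measures look at lows.** This also stands in part. A reader might infer that repeated lows could not show anywhere in the trial. That goes too far: CGM time below 70 mg/dL is in the same outcome, would rise with repeated or long lows, and is compared between groups. The halting rule considers numbers of severe events. The cover is partial, because CGM is optional and depends on funding, and time below a threshold is not an event count.

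**The clause may not be an episode rule.** It is tempting to call it an episode rule that the plan fails to use. The text does not say so, and a window on both sides of the index event fits a rule for opening an episode imperfectly. What can be said is that it is undefined.

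**The example is chosen to give zero difference.** True. If early glargine also raised the share of children with any low, the percent of patients could move, though chi-squared power at 24 per arm is only 16% for 10% v 20% and 32% for 20% v 40%.

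**Counting episodes would not settle the question either.** True at this sample size, as the interval of about 0.9 to 7 shows. That argues for adding the count beside the percent of patients, not for replacing it.

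**Conclusion.** The point holds in a limited form. The aim is stated in event frequency, the only hypoglycemia measure for all participants is per patient, the +/- 2 h clause is undefined, and no measure counts all lows in all participants. On the glucometer measure alone, a two- to three-fold higher episode rate confined to the same share of children would appear as a 0-point difference. That figure rests on assumptions about how many children have a low and how often lows recur; the documents supply neither. The mismatch of units and the missing definition can be read directly from the text. This concerns a secondary outcome and can be put right by wording and one added analysis.

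**What to change.** In Section IV.A, outcome 3:

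1. State what the +/- 2 h clause means. For example: glucometer values below 70 mg/dL within 2 h of an index low belong to one episode, and a later low opens a new one. Say how a run of low readings longer than 2 h is counted.
2. Keep the percent of patients with at least one low as the measure of risk.
3. Add the number of episodes per child by arm as the measure of event frequency for Aim 3a, with a rate ratio and 95% CI from a count model with robust variance, or a permutation test. Name this in Section VII.
4. Report the IV-insulin period and the 12 h after it separately. Glucose is measured hourly in the first (Section IV.C.2.1) and only before meals, at bedtime and at 0200 in the second (Section IV.C.2.2), so episode counts are not comparable across the two.

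**Cost:** outcome wording and one extra analysis of values already recorded. The interval will be wide at 24 per arm. The plan should therefore report the estimate with its interval and say that a non-significant result does not show that events are not increased.

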- Upon diagnosis of DKA patients will begin rehydration with standard fluid therapy using an initial IV bolus of 10mL/kg of 0.9% saline.
- Fluid boluses may be repeated at the discretion of the treating physician to restore hemodynamic instability.
- During initial therapy, study personnel will obtain informed consent. .
- Participant Data: basic information such as name, date of birth, race/ethnicity, and diagnosis will be collected.
- Randomization:
 - We will use a blocked, stratified randomization scheme to allocate participants 1:1 to treatment groups. Randomization will be stratified within new onset and existing T1D patients to ensure balance across treatment groups.
 - Ideally, randomization will occur during the initial fluid bolus, however, if this is not possible then the patient will be treated with the standard DKA protocol for this study site until consent is completed, but not beyond the time frame outlined in the exclusion criteria.
 - Participants will be randomized into one of two groups:
 - 1. Early glargine, study group (N ~ 25):**
 - a. Administer glargine SQ x 1 when pH \geq 7.10.
 - b. Primary investigator and/or on-call co-investigator to determine glargine dose:
 - i. New onset T1D: 0.3 units/kg
 - ii. Established T1D: use home total daily dose (TDD) of long-acting insulin (or TDD of basal if on an insulin pump), converted to glargine equivalents.
 - 2. Standard-of-care, control group (N ~ 25):**
 - a. Administer glargine SQ x 1 at time of correction of acidosis (venous pH \geq 7.3 and serum bicarbonate \geq 18 or BHB \leq 1) and discontinuation of IV insulin.
 - b. Primary investigator and/or on-call co-investigator to determine glargine dose as described above.
- After initial fluid bolus(es), standard insulin therapy begins with a continuous infusion of IV regular insulin at a rate of 0.1 units/kg/hr.
- Ongoing rehydration is established using IV fluids with $\frac{3}{4}$ normal saline at a standard rate of 1.5 x maintenance unless this is determined to be harmful by the primary attending physician.
- Potassium replacement is provided using IV fluids containing potassium acetate and potassium phosphate.
- When serum glucose concentration declines below 250 mg/dL, dextrose (5-12.5%) is added to the IV fluids to maintain serum glucose between 100 mg/dL and 200 mg/dL.

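### Later time bins of the glucose-fall outcome are measured while dextrose holds glucose in range, so a null result there is not evidence for Hypothesis 3b

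*Combined protocol and SAP*

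**What the plan says.** Section I, Hypothesis 3b, states: "Rate of blood glucose decrease while on IV insulin in children with DKA will not be different" between the arms. It gives no margin.

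Section IV.A, secondary outcome 4, is the "Rate of blood glucose decrease while on IV insulin on glucometer and CGM within the following time points": 0-2, 2-4, 4-6 and >6 hours. It covers all time on IV insulin. Time zero is not defined and the last bin is open-ended.

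Section IV.C.2.1 sets the fluid rule: "When serum glucose concentration declines below 250 mg/dL, dextrose (5-12.5%) is added to the IV fluids", with the aim "to maintain serum glucose between 100 mg/dL and 200 mg/dL". If dextrose above 12.5% would be needed, the IV insulin rate is lowered.

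The plan does not end outcome 4 at dextrose start, adjust it for dextrose, or make dextrose requirement an outcome. The data list in section IV.D does not name dextrose. Section VII gives no analysis for the binned rate; its mixed models concern CGM summaries per patient and day. Outcome 5 counts children whose IV insulin rate was lowered, which under the fluid rule is the step after dextrose reaches its ceiling.

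**The concern.** Once dextrose is being titrated, glucose is a controlled quantity. Extra insulin action then appears mainly as more dextrose and much less as a faster fall. The arm that falls faster reaches 250 mg/dL sooner, so it spends more of each later bin under control and can show the slower fall there. The later bins also contain only children still on IV insulin, and section II cites a retrospective pediatric review in which early glargine shortened IV insulin.

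Hypothesis 3b belongs to the hypoglycemia safety aim and predicts no difference, so attenuation in the later bins pushes towards the expected conclusion. Sections III and IV.B give cerebral edema and hypoglycemia in children as reasons why adult data cannot simply be carried over. A falsely reassuring reading would therefore matter.

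**Working it through.** **The plan's own figure.** The plan states no figure for outcome 4. The only sized outcome is the primary one (section VII: 30% v 70%, alpha 0.05 taken as two-sided, 80% power). Per arm, n = [1.96 × √(2 × 0.5 × 0.5) + 0.8416 × √(0.3 × 0.7 + 0.7 × 0.3)]² / 0.4² = 1.931² / 0.16 = 23.3, rounded up to 24. The total is 48, as stated. Nothing below changes it.

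**Inputs from the documents.** Dextrose trigger 250 mg/dL; target 100-200 mg/dL; the four bins; hourly glucose on IV insulin; entry glucose from 200 mg/dL; early glargine given when pH reaches 7.10; up to 6 hours of IV insulin allowed before enrolment.

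**Assumed, because the documents do not give them.** Start glucose, rate of fall, size of the glargine effect, its onset, and how tightly titration controls glucose.

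**One worked path.** Before 250 mg/dL, G falls linearly at rate r. After 250 is reached at time h, G(t) = 175 + 75 × exp(−(t − h)), that is, a draw towards 175 mg/dL with a 1-hour time constant. Bin rate = [G(a) − G(b)] / (b − a). Start 450 mg/dL; underlying fall 60 (control) v 90 (early) mg/dL/h.

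- Control: h = 200/60 = 3.33 h; G(2) = 330, G(4) = 213.5, G(6) = 180.2.
- Early, acting from hour 0: h = 200/90 = 2.22 h; G(2) = 270, G(4) = 187.7, G(6) = 176.7.
- Early, acting from hour 2: h = 2 + 80/90 = 2.89 h; G(2) = 330, G(4) = 199.7, G(6) = 178.3.

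| Bin | Control (mg/dL/h) | Early, onset 0 h | Difference | Early, onset 2 h | Difference |
|---|---|---|---|---|---|
| 0-2 h | 60.0 | 90.0 | +30.0 | 60.0 | 0 |
| 2-4 h | 58.2 | 41.2 | −17.1 | 65.2 | +6.9 |
| 4-6 h | 16.6 | 5.5 | −11.2 | 10.7 | −6.0 |

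The 2-4 h sign depends on onset. The 4-6 h bin is reversed in both cases.

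**A wider grid.** Start 300, 400, 500, 600 or 700 mg/dL; control fall 50, 75 or 100 mg/dL/h; early fall 25% faster from hour 0, 2 or 4. Titration draws glucose towards 150 mg/dL with a 1.5-hour time constant, never faster than the underlying fall. The >6 h bin is taken as 6-10 h. This gives 5 × 3 × 3 = 45 scenarios. Cancelled means a difference within 0.5 mg/dL/h.

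| Bin | Onset | Faster fall still seen | Cancelled | Reversed |
|---|---|---|---|---|
| 0-2 h | 0 h | 15 | 0 | 0 |
| 2-4 h | 0 h | 6 | 0 | 9 |
| 2-4 h | 2 h | 10 | 5 | 0 |
| 4-6 h | all 45 | 11 | 16 | 18 |
| >6 h | all 45 | 1 | 20 | 24 |

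Before onset the early bins show no difference, because glargine is not yet acting. Targets of 100-200 mg/dL and time constants of 0.5-3 h gave a similar pattern.

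**A mixed population.** In a simulation with mean start 500 (SD 130) mg/dL, mean fall 75 (SD 20) mg/dL/h and a 25% effect, the mean differences across the four bins were +15.0, +0.5, −6.3 and −3.6 mg/dL/h for onset at hour 0. For onset at 2 h they were 0, +7.7, −1.5 and −2.3.

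**Checking the remedy.** A slope from hour 0 to 250 mg/dL can itself be diluted. With start 600, 60 v 90 mg/dL/h and onset 2 h, 250 is reached at 2 + 230/90 = 4.56 h. The slope from hour 0 is 350/4.56 = 76.8, a difference of +16.8, while the planned 2-4 h bin shows the full +30.0. Starting the slope at hour 2 in both arms gives 90 v 60, so +30 is recovered. This is why the bins should stay and the slope needs a second starting point.

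**The case against.** **Certainty.** A reader might infer that a faster fall will always be cancelled, or that the outcome as a whole cannot detect one. The documents do not support that. The bins keep the early hours separate; 0-2 h shows the full difference in the worked path if glargine acts from the start, and 11 of 45 scenarios keep a positive difference at 4-6 h. Nor should the bins be pooled into one average over the first six hours to show that the effect vanishes, because the plan defines no such outcome. This objection stands, and the conclusion below is conditional for that reason.

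**Effect size.** The new-onset glargine dose in the plan, 0.3 units/kg over a stated 20-24 h action, averages 0.3/24 = 0.0125 to 0.3/20 = 0.015 units/kg/h. That is 12.5-15% of the 0.1 units/kg/h infusion. If the fall scales with insulin rate (a simplification), the assumed 25-50% is generous. This bears on size more than on mechanism. At 15% (60 v 69) in the worked path with onset at hour 0, h = 200/69 = 2.90 h, G(2) = 312, G(4) = 199.9 and G(6) = 178.4. The early rates are 69.0, 56.0 and 10.8, so the differences are +9.0, −2.2 and −5.9.

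**Estimand.** The fall under protocol care, dextrose included, is a legitimate quantity: it is what the child experiences. This stands as a reason to keep and report the bins. It does not make a null later bin evidence that early glargine adds no glucose-lowering effect.

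**Other outcomes.** Outcomes 3 and 5 capture part of the safety signal. Neither shows a rise in dextrose below the 12.5% ceiling.

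**Conclusion.** The concern holds in conditional form. Outcome 4 runs through the period when descent is controlled by dextrose, and the plan has no rule for it. A faster fall under early glargine can therefore be attenuated or reversed in bins after dextrose starts. Under the stated assumptions this is nearly always so at >6 h (44 of 45 scenarios) and often so at 4-6 h (34 of 45). At 2-4 h it turns on start glucose, fall rate and glargine onset.

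The 0-2 h bin is largely intact only if glargine is already acting. That is uncertain, because the dose waits for pH 7.10, prior IV insulin is allowed and time zero is undefined. Entry from 200 mg/dL also means that some children can be under titration from the first bin.

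The mechanism follows from the text alone; every magnitude rests on assumed inputs. The consequence is limited to one part of a secondary safety aim: no difference in the later bins must not be read as support for Hypothesis 3b. The primary outcome is untouched.

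**What to change.** These are analysis changes only, with no change to treatment.

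1. Keep the planned bins and define time zero (for example, the start of IV insulin).
2. Add a pre-dextrose slope, ending at the first of dextrose start or IV insulin stop, compared between arms with adjustment for glucose at the start of the slope. Start it at time zero or, so that pre-glargine hours do not dilute it, at the time pH is first at or above 7.10, applied identically in both arms.
3. Compare dextrose requirement while on IV insulin between arms, with 95% confidence intervals: for example, the highest concentration used and the proportion of IV insulin time above 5% dextrose. Use a proportion and not hours, because hours depend on how long IV insulin runs.
4. State that bins after dextrose start describe glucose under titration and will not be used to support Hypothesis 3b.

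Cost: dextrose concentrations and times must be extracted from the chart; glucose and pH are already scheduled. Children below 250 mg/dL at the chosen start contribute no slope, and a short interval before dextrose gives an imprecise slope with hourly readings, so the number contributing should be reported by arm. Because glargine's action follows its injection, some dilution may remain even with the pH-based start.
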